3.2 Exclusion Criteria

- 3.21 Diagnosed or treated for another malignancy ≤ 2 years prior to registration or previously diagnosed with another malignancy and have any evidence of residual disease.
NOTE: If there is a history or prior malignancy, patient must not be receiving other specific treatment for their cancer. Patients with non-melanoma skin cancer or carcinoma in situ of any type, or low-risk prostate cancer after curative therapy, are not excluded if they have undergone complete resection.
NOTE: Platelet transfusions to help patients meet eligibility criteria are not allowed ≤ 3 days prior to study registration.
- 3.22 Any of the following because this study involves an investigational agent whose genotoxic, mutagenic and teratogenic effects on the developing fetus and newborn are unknown:
 - Pregnant persons
 - Nursing persons
 - Persons of childbearing potential who are unwilling to employ adequate contraception
- 3.23 Co-morbid systemic illnesses or other severe concurrent disease which, in the judgment of the investigator, would make the patient inappropriate for entry into this study or interfere significantly with the proper assessment of safety and toxicity of the prescribed regimens. **NOTE:** this includes uncompensated heart or lung disease.
- 3.24 Receiving any other investigational agent which would be considered as a treatment for the primary neoplasm. **NOTE:** Bisphosphonates are considered to be supportive care rather than therapy and are allowed while on protocol treatment.
- 3.25 Patient has \geq Grade 2 peripheral neuropathy, or Grade 1 with pain on clinical examination during the screening period.

- 3.26 Major surgery ≤ 14 days prior to registration.
- 3.27 Systemic treatment with strong CYP3A inducers (rifampin, rifapentine, rifabutin, carbamazepine, phenytoin, phenobarbital) or use of Ginkgo biloba or St. John's wort ≤ 14 days prior to registration.
- 3.28 Uncontrolled intercurrent illness including, but not limited to, ongoing or active infection, symptomatic congestive heart failure, unstable angina pectoris, cardiac arrhythmia, or psychiatric illness/social situations that would limit compliance with study requirements. **NOTE:** Any ECG abnormality at screening must be documented by the investigator as not medically relevant.
- 3.29a QTc > 470 milliseconds (msec) on a 12-lead ECG obtained during the Screening period.

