8.11 Instruction for initiation of a new cycle of therapy

A new cycle of treatment may begin on the scheduled Day 1 of a new cycle if:

- The ANC is $\geq 1.0 \times 10^9/L$ (=1000/microliter)
- The platelet count is $\geq 75 \times 10^9/L$ unless the participant has $\geq 50\%$ bone marrow infiltration in which case a platelet count of $\geq 50 \times 10^9/L$ is allowed
- Any other non-hematologic treatment -related adverse event that may have occurred has resolved to \leq Grade 1 or baseline severity.

If these conditions are not met on Day 1 of a new cycle, the subject will be evaluated weekly and a new cycle of therapy will be held until the toxicity has resolved as described below

If any drug dosing was halted during the previous cycle and was restarted with a one-level dose reduction without requiring an interruption for the remainder of the cycle, then that reduced dose level will be initiated on Day 1 of the new cycle.

If any drug dosing was omitted for the remainder of the previous cycle or if the new cycle is held due to known hematologic toxicity newly encountered on the scheduled Day 1, then the new cycle will be started with a one-level dose reduction. If a new cycle of therapy cannot be restarted within 4 weeks of the scheduled Day 1 due to non-resolution of drug related toxicities, the patient will be removed from protocol therapy and will go to event monitoring.

→ → Use the NCI Common Terminology Criteria for Adverse Events (CTCAE) version 4.0* unless otherwise specified ← ←

8.2 Dose modifications for ixazomib based on adverse events during a cycle (for each cycle during induction and consolidation and maintenance)

CTCAE System/Organ/Class (SOC)	ADVERSE EVENT	AGENT[#]	ACTION^{**}
Blood and lymphatic system disorders	Febrile neutropenia If platelet count $<30 \times 10^9/L$ or ANC $<1.0 \times 10^9/L$ or ANC $>1.0 \times 10^9/L$ (up to LLN) with fever (temperature $>38.5^\circ C$)	Ixazomib	Days 2-15: Ixazomib dose should be omitted. Complete blood count (CBC) with differential should be followed weekly. If ANC is $\geq 1.0 \times 10^9/L$ and/or platelet counts $\geq 30 \times 10^9/L$, ixazomib may be reinitiated with 1 dose level reduction (see Table 8.1). The subsequent cycle will use the reduced dose
Nervous System Disorders	Peripheral motor neuropathy OR Peripheral sensory neuropathy Newly developed Grade 1 with pain or \geq Grade 2	Ixazomib	Reduce dose of ixazomib to the next lower dose level

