	Grade 2 with pain or Grade 3	Ixazomib	Omit ixazomib until AE resolves or returns to baseline. When AE resolves, re-initiate ixazomib at the next lower dose level.
	Grade 4	Ixazomib	Omit ixazomib. Peripheral neuropathy should be monitored until toxicity resolves or returns to baseline. Upon recovery, if the patient has received clinical benefit from therapy with ixazomib, the investigator may consider restarting ixazomib at the next lower dose level
Skin and subcutaneous tissue disorders	Rash, maculo-papular Rash, acneiform Grade 2 or 3	Ixazomib	Omit ixazomib until rash resolves to \leq Grade 1 (See Section 9.9a). Restart at same dose. If the rash recurs, reduce dose by one dose level.
	Grade 4		Discontinue ixazomib

CTCAE System/Organ/Class (SOC)	ADVERSE EVENT	AGENT[#]	ACTION^{**}
Other	Any other non-hematological Grade 3 attributable adverse event except:	Ixazomib Pomalidomide Dexamethasone	Omit ixazomib or pomalidomide or both depending on the attribution to either or both drugs, until resolution to Grade ≤1 or baseline. Restart at next lower dose - If a patient is already at the lowest drug level, go to event monitoring. If the toxicity can be attributed to either of the drugs, pomalidomide should be discontinued at first instance followed by ixazomib for recurrence of the same toxicity necessitating dose modification.
Gastrointestinal Disorders	Grade 3 nausea and/or emesis in the absence of optimal anti-emetic prophylaxis Grade 3 diarrhea that occurs in the absence of optimal supportive therapy		
General disorders and administration site conditions	Grade 3 fatigue (consider relatedness to one or all of the components of the combination)		
Other	Grade 4 Nonhematologic adverse events (consider relatedness to one or all of the components of the combination)	Ixazomib Pomalidomide Dexamethasone	Consider permanently discontinuing ixazomib or pomalidomide or dexamethasone or all three depending on the attribution to either one, two or all three drugs (exception would be if the investigator determines the patient is obtaining a clinical benefit) If both ixazomib and pomalidomide are discontinued, the patient will go to event monitoring.

* Located at http://ctep.cancer.gov/protocolDevelopment/electronic_applications.ctc.htm

** Use the following to describe actions in the Action column:

- Omit = The current dose(s) for the specified drug(s) during a cycle is skipped. The patient does not make up the omitted dose(s) at a later time

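### The first neuropathy row in Table 8.2 has no upper grade limit, so Grade 2 with pain, Grade 3 and Grade 4 match both a reduce and an omit instruction for ixazomib

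*Combined protocol and SAP*

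**What the plan says.** Table 8.2 (Section 8.2) applies to ixazomib in induction, consolidation and maintenance. For motor or sensory neuropathy it has three rows.

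- **Row 1.** The trigger is "Newly developed Grade 1 with pain or" Grade 2 or higher (the cell uses a greater-than-or-equal sign). The action is "Reduce dose of ixazomib to the next lower dose level". No interruption is mentioned.
- **Row 2.** The trigger is "Grade 2 with pain or Grade 3". The action is "Omit ixazomib until AE resolves or returns to baseline", followed by "When AE resolves, re-initiate ixazomib at the next lower dose level".
- **Row 3.** The trigger is Grade 4. Ixazomib is omitted, and "Peripheral neuropathy should be monitored until toxicity resolves or returns to baseline". After recovery the investigator may consider restarting one level lower if the patient has benefited.

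The notes under the table define omit: "The current dose(s) for the specified drug(s) during a cycle is skipped", and the dose is not made up later. Section 8.0 makes the table binding in the first two cycles and treats it as guidance after that. Exclusion 3.25 bars patients with Grade 2 or higher neuropathy, or "Grade 1 with pain on clinical examination during the screening period".

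**The concern.** Every event of Grade 2 with pain, Grade 3 or Grade 4 is also Grade 2 or higher, so it falls under row 1 as well as row 2 or row 3. The actions differ. Reducing, taken alone, lets dosing go on at a lower level during the event. Omitting stops dosing until recovery. A site that reads row 1, finds its patient covered and goes no further could give reduced Day 8 and Day 15 ixazomib during painful Grade 2 or Grade 3 neuropathy, and would believe it was following the table. Neuropathy is an expected toxicity: Table 1-3 lists it in 45 of 173 patients (26%), all grades, in the oral combination studies.

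The cell looks like a drafting slip. Neighbouring entries bound their grades: rash in Table 8.2 is split into Grades 2 or 3 and Grade 4, sensory neuropathy in Table 8.3 into Grade 3 and Grade 4, and dyspepsia in Table 8.4 into Grades 1 to 2 and Grade 3 or higher.

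**Working it through.** **Step 1: match each state to the three neuropathy rows.** The plan states no figure to reproduce here. The inputs are the three triggers.

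| State | Rows matched now | Rows matched after the fix |
|---|---|---|
| Grade 1, no pain | none | none |
| Grade 1 with pain | 1 | 1 |
| Grade 2, no pain | 1 | 1 |
| Grade 2 with pain | 1 and 2 | 2 |
| Grade 3 | 1 and 2 | 2 |
| Grade 4 | 1 and 3 | 3 |

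Row 1 covers five states, and three of the five match two rows. After the fix none of the five does, counting only these three rows.

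**Step 2: look for text that settles the overlap.**

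- *Newly developed.* Exclusion 3.25 removes patients who already have a qualifying state at screening. Any first qualifying event is therefore new, and the phrase does not separate the rows.
- *Greatest-reduction rule (Section 8.0).* It covers several adverse events occurring together, not one event that matches two rows.
- *New-cycle conditions (Section 8.11).* They hold Day 1 of the next cycle until the event is Grade 1 or less or back to baseline. They do not govern Days 8 and 15 of the current cycle.
- *One-drug note (under Table 8.2).* It decides which drug is reduced when both are implicated, not whether to reduce or omit.
- *Row precedence.* No text states it.

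**Step 3: size the difference in one cycle.** The dose levels come from Section 8.1: 4 mg, 3 mg, 2.3 mg (each on Days 1, 8 and 15), then 2.3 mg on Days 1 and 15 only, then discontinue. The difference is the ixazomib given under row 1 alone minus the ixazomib given when the rest of the cycle is omitted. It assumes that the reduction takes effect at the next dose, that ixazomib is the drug reduced, and that the event does not resolve within the cycle.

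| Level at onset | Onset after Day 1 dose | Onset after Day 8 dose |
|---|---|---|
| 4 mg | (4+3+3) − 4 = 6 mg | (4+4+3) − (4+4) = 3 mg |
| 3 mg | (3+2.3+2.3) − 3 = 4.6 mg | (3+3+2.3) − (3+3) = 2.3 mg |
| 2.3 mg | (2.3+0+2.3) − 2.3 = 2.3 mg | (2.3+2.3+2.3) − (2.3+2.3) = 2.3 mg |
| 2.3 mg, Days 1 and 15 | 0 (next level is discontinue) | 0 |

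A full cycle at 4 mg is 3 × 4 = 12 mg, so 6 mg is 6/12 = 50% and 3 mg is 3/12 = 25%. With onset after the Day 15 dose the difference is 0. It is also 0 whenever the site omits and restarts lower.

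**The case against.** The strongest reply is that rows 2 and 3 sit directly below row 1 and name the exact grades. Following a table strictly means applying every row that matches, and a site that stops at row 1 breaches row 2 or row 3. Omitting and then restarting one level lower satisfies all matching rows, and rows 1 and 2 end at the same dose. This stands as the likely intent, and it keeps the point minor. It does not make row 1 correct as worded.

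A reader might infer that the protocol directs sites to keep dosing through Grade 3 or 4 neuropathy, or that the rows cannot be reconciled. The documents support neither, because one course of action meets every row.

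A reader might also take Grade 4 as the main danger. It is largely covered elsewhere. The general Grade 4 non-hematologic row in Table 8.2 tells the investigator to consider permanent discontinuation, and Table 8.3 takes patients with Grade 4 sensory neuropathy off all study treatment. The cover is incomplete: the first provision is discretionary, and the second is a pomalidomide rule that does not name motor neuropathy. Neither reaches Grade 2 with pain or Grade 3. The general Grade 3 row is for other events, and neuropathy has its own rows.

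Timing narrows the scenario further. In the Section 4.1 calendar the Day 8, 15 and 22 column carries only a blood count, which may be done at an outside facility. Adverse event review and physical examination are scheduled before each cycle, which is when Section 8.11 applies. Mid-cycle grading therefore depends mostly on patients reporting symptoms between visits. That is possible, but it is not the scheduled route.

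Finally, 6 mg is not a general upper bound. When an event is attributed to both drugs, the note under Table 8.2 starts with pomalidomide, and the figure does not describe that case.

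**Conclusion.** Row 1 is wrong as written: it is broader than it should be and overlaps rows 2 and 3 for three of its five states. This is a minor patient-safety point, mainly about Grade 2 with pain and Grade 3. The largest calculated excess at the 4 mg dose is 6 mg of 12 mg in one cycle, under all the conditions in Step 3 and only if row 1 is used alone and the event is graded between the scheduled pre-cycle assessments. Section 8.11 then holds the next cycle.

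No probability can be attached. Table 1-3 gives neuropathy for all grades only, and three of five counts table states, not patients. The primary endpoint, the rule of at least 14 successes in 21 patients, the significance level, the power and the sample size are unaffected.

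**What to change.** In row 1 of the neuropathy entry in Table 8.2, keep the Grade 1 with pain trigger and replace Grade 2 or higher with Grade 2 without pain. Leave rows 2 and 3 as they are. Each neuropathy state that triggers an action then matches only one of the three rows.

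The cost is a wording change to one cell at the next amendment, with no change to the design or analysis. The edit does not settle how row 3's optional restart fits with the Table 8.3 removal rule for Grade 4 sensory events, or whether the general Grade 4 row also applies to neuropathy.

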8.0 Dosage Modification Based on Adverse Events

Strictly follow the modifications in this table for the first **two** cycles, until individual treatment tolerance can be ascertained. Individual drugs can be dose reduced as per the table below depending on the adverse event attribution. Thereafter, these modifications should be regarded as guidelines to produce mild-to-moderate, but not debilitating, side effects. If multiple adverse events are seen, administer dose based on greatest reduction required for any single adverse event observed. Reductions apply to treatment given in the preceding cycle and are based on adverse events observed since the prior dose.

NOTE: If either of pomalidomide or ixazomib is discontinued, the patient can continue on the other drugs, unless specified otherwise in the dose modification tables. If both are discontinued, the patient will go to event monitoring (Section 18.0).

ALERT: *ADR reporting may be required for some adverse events (See Section 10)8.1*

Dose Levels for each drug in the combination

(Based on Adverse Events in Tables 8.2-4)

NOTE: One drug can be reduced each time based on the drug most likely related to the toxicity observed.

Ixazomib (Days 1, 8, 15)		Pomalidomide (Day 1-21)		Dexamethasone (Days 1, 8, 15, 22)	
Starting dose	4 mg	Starting dose	4 mg	Starting dose	40 mg
-1	3 mg	-1	3 mg	-1	20 mg
-2	2.3 mg	-2	2 mg	-2	12 mg
-3	2.3 mg Days 1, 15	-3	1 mg	-3	4 mg
-4	Discontinue	-4	Discontinue	-4	Discontinue

If patients cannot tolerate dose level –3 of ixazomib AND pomalidomide they will go to event monitoring per Section 4.2. If dexamethasone is discontinued, the patient may continue treatment.

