8.3 Dose modifications for pomalidomide based on adverse events during a cycle

(For each cycle during induction and consolidation and maintenance)

Table 8.3			
CTCAE System/Organ/Class (SOC)	ADVERSE EVENT	AGENT	ACTION**
Investigations	Neutrophil count decreased If ANC $<1.0 \times 10^9/L$ or ANC $>1.0 \times 10^9/L$ (up to LLN) with fever (temperature $>38.5^\circ C$)	Pomalidomide	Omit pomalidomide dose. Follow CBC weekly. If neutropenia has resolved to \leq Grade 2 prior to Day 21 and fever has resolved, restart pomalidomide at next lower dose level and continue through Day 21 of a 28-day cycle. If febrile neutropenia is the only toxicity for which a dose reduction is required, G-CSF may be used and the pomalidomide dose maintained.
Investigations	Platelet count decreased If platelet count $<30 \times 10^9/L$	Pomalidomide	Omit pomalidomide dose Follow CBC weekly Hold anticoagulation/antiplatelet therapy until platelets $\geq 50,000/mm^3$ If platelet count resolves to \leq Grade 2 prior to Day 21, restart pomalidomide at next lower dose level and continue through Day 21 of each cycle
Skin and subcutaneous tissue disorders	Rash maculopapular Grade 2 or 3	Pomalidomide	Omit pomalidomide dose; follow weekly If the AE resolves to \leq Grade 1 prior to Day 21, restart pomalidomide at next lower dose level and continue through Day 21 of each cycle
	Grade 3-4 Stevens –Johnson Syndrome	Pomalidomide	Discontinue pomalidomide and remove patient from all study treatment
	\geq Grade 3 Erythema multiforme	Pomalidomide	Discontinue pomalidomide and remove patient from all study treatment

Table 8.3			
CTCAE System/Organ/Class (SOC)	ADVERSE EVENT	AGENT	ACTION**
	Erythroderma ≤Grade 3	Pomalidomide	Omit pomalidomide dose; follow weekly If the AE resolves to ≤Grade 1 prior to Day 21, restart pomalidomide at next lower dose level and continue through Day 21 of the 28-day cycle
	Rash, maculo-papular Rash, acneiform Grade 4	Pomalidomide	Discontinue pomalidomide and remove patient from all study treatment
Nervous system disorders	Peripheral sensory neuropathy Grade 3	Pomalidomide	Omit pomalidomide dose and follow at least weekly. If the AE resolves to ≤Grade 1 prior to Day 21, restart pomalidomide at next lower dose level and continue through Day 21 of the 28-day cycle
	Peripheral sensory neuropathy Grade 4	Pomalidomide	Discontinue pomalidomide and remove patient from all study treatment

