Immune system disorders	Allergic reaction Grade 2-3	Pomalidomide	Omit dose and follow at least weekly If the AE resolves to ≤Grade 1 prior to Day 15, restart at next lower dose level and continue through Day 21 of the 28-day cycle
	Allergic reaction Grade 4	Pomalidomide	Discontinue pomalidomide and remove patient from all study treatment
Vascular disorders	Thromboembolic event ≥ Grade 3	Pomalidomide	Omit dose and start anticoagulation Restart at investigator's discretion (maintain dose level)
Endocrine disorders	Hyperthyroidism or Hypothyroidism ≥ Grade 2	Pomalidomide	Omit pomalidomide for remainder of cycle, evaluate etiology, and initiate appropriate therapy See Instructions for Initiation of a New Cycle and reduce the dose of pomalidomide by 1 dose level.

Table 8.3			
CTCAE System/Organ/Class (SOC)	ADVERSE EVENT	AGENT	ACTION**
Other non-hematologic adverse event	Other non-hematologic \geq Grade 3	Pomalidomide	If the AE can be attributed to either of the drugs, pomalidomide should be discontinued at first instance followed by ixazomib for recurrence of the same toxicity necessitating dose modification Omit pomalidomide dose. Follow at least weekly If the toxicity resolves to \leq Grade 2 prior to Day 21, restart pomalidomide at next lower dose level and continue through Day 21 of the 28-day cycle

* Located at http://ctep.cancer.gov/protocolDevelopment/electronic_applications.ctc.htm

** Use the following to describe actions in the Action column:

- Omit = The current dose(s) for the specified drug(s) during a cycle is skipped. The patient does not make up the omitted dose(s) at a later time
- Hold/Delay = The current dose(s) of all drugs during a cycle is delayed. The patient does make up the delayed dose(s) when the patient meets the protocol criteria to restart drugs.
- Discontinue = The specified drug(s) are totally stopped.

NOTE: For adverse events attributable to both ixazomib and pomalidomide, only one of the drugs should be reduced for each incidence of toxicity severe enough to necessitate dose reduction. The drug reduced should alternate starting with pomalidomide for the first dose reduction.

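### TEN and DRESS, listed risks of both ixazomib and pomalidomide, have no row in either dose-modification table and so fall into default rows that allow a restart; SJS attributed to ixazomib alone is ambiguous between the tables

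*Combined protocol and SAP*

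**What the plan says.** Section 15.17 places SJS, TEN and DRESS among the rare, serious risks of ixazomib. Section 15.27 lists the same three for pomalidomide, with no frequency given.

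Table 8.2 (ixazomib) names only maculo-papular and acneiform rash under skin; its Grade 4 action is "Discontinue ixazomib". Non-hematologic events without their own row go to the rows labelled Other. The Grade 3 row covers "Any other non-hematological Grade 3 attributable adverse event except" nausea or vomiting without optimal prophylaxis, diarrhea without optimal supportive therapy, and fatigue. The drug or drugs blamed are withheld until the event returns to Grade 1 or below, or to baseline. The instruction is then "Restart at next lower dose - If a patient is already at the lowest drug level, go to event monitoring". The Grade 4 row says "Consider permanently discontinuing ixazomib or pomalidomide or dexamethasone or all three depending on the attribution to either one, two or all three drugs", and adds that an "exception would be if the investigator determines the patient is obtaining a clinical benefit".

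Table 8.3 (pomalidomide) has rows for Grade 3-4 SJS, for erythema multiforme of Grade 3 or above, and for Grade 4 maculo-papular or acneiform rash. The action for each is "Discontinue pomalidomide and remove patient from all study treatment". Its heading extends the table to induction, consolidation and maintenance. It has no row for TEN or DRESS. Its default row, for other non-hematologic events of Grade 3 or above, lets pomalidomide restart one level lower once the event is Grade 2 or below before Day 21. Where either drug could be responsible, it says "pomalidomide should be discontinued at first instance followed by ixazomib for recurrence of the same toxicity necessitating dose modification"; the Grade 3 default in Table 8.2 has the same rule.

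Section 8.0 ties modification to causation: "Individual drugs can be dose reduced as per the table below depending on the adverse event attribution". It makes the tables strict for the first two cycles and guidance after that.

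**The concern.** A dose-modification table matters most for the events after which a patient should not be re-exposed. The protocol itself describes these skin reactions as life-threatening in 15.17. Yet for TEN and DRESS the written default is the one used for any ordinary severe toxicity: wait, lower the dose, resume. What is at stake is the safety of an individual patient. Where investigators follow the table as written, the patient could be given again the drug blamed for the reaction.

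The plan is also inconsistent with itself. It requires a stop for a Grade 4 common rash and, in Table 8.3, for Grade 3-4 SJS, but not for two reactions that it lists beside SJS for both drugs.

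**Working it through.** No arithmetic decides this point. The check is to follow each event through the two tables.

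| Event | Table 8.2 (ixazomib) | Table 8.3 (pomalidomide) |
|---|---|---|
| Maculo-papular or acneiform rash, Grade 4 | Own row: ixazomib must stop | Own row: all study treatment ends |
| SJS, Grade 3-4 | No row; default rows | Own row: all study treatment ends |
| TEN or DRESS, where graded 3 | No row; default: withhold to Grade ≤1 or baseline, restart one level lower | No row; default: withhold, restart one level lower at Grade ≤2 before Day 21 |
| TEN or DRESS, Grade 4 | No row; default: consider stopping, clinical-benefit exception | No row; same default row, which covers Grade ≥3 |

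1. **TEN and DRESS.** Neither is among the exceptions to the Grade 3 default in Table 8.2, so that default applies. Table 8.3 sends them to its own default. In both tables, the Grade 4 action for TEN and DRESS is looser than the Grade 4 action for a common rash.

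2. **Either drug possible.** This is the likely situation in combined dosing, since both drugs list both reactions. The rule stops pomalidomide first and ixazomib only if the same toxicity returns. Read literally, a second episode of TEN or DRESS is needed before ixazomib is stopped for good.

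3. **SJS.** Ending all study treatment includes ixazomib, and the heading of Table 8.3 reaches into maintenance. But the row names pomalidomide as the agent, and 8.0 makes action follow attribution. For a case attributed to ixazomib alone, one reading applies the Table 8.3 row and another applies the Table 8.2 defaults. The ambiguity matters chiefly from cycle 10 on, when ixazomib is the only scheduled drug (7.2) and there is no pomalidomide to discontinue.

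4. **Supportive-care text.** The rash subsection numbered 9.9a has SJS managed symptomatically in line with usual medical practice. It does not instruct a stop. Its sentence on re-starting at a reduced level concerns rash in general and comes before the SJS sentence, so it is not an order to rechallenge after SJS.

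5. **Reach.** Combined-drug cycles are 4 (induction, cycles 1-4) + 4 (consolidation, cycles 6-9) = 8. The tables are strict in 2 of these 8 and are guidance in the other 6 and in maintenance. The planned total is 25 patients (16.22). The documents give no event rate for these reactions, so no expected number of cases is calculated.

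**The case against.** The strongest reply is that the protocol leaves ample room to stop. Section 13.4 lets the investigator end treatment at any cycle for an adverse event or in the patient's best interests, and nothing in 8.0 overrides it. After cycle 2 the tables are guidance meant to keep side effects mild to moderate, which itself argues against rechallenge after such a reaction. Under 8.11, drug-related toxicity that keeps a new cycle from starting within 4 weeks ends protocol therapy. In Table 8.2 a patient already at the lowest level goes to event monitoring. Maintenance ends at unacceptable toxicity (7.2). All of this stands and lowers the severity. None of it, however, requires ixazomib to stop once the reaction has resolved.

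At Grade 4, the line in the skin block of Table 8.2 does not repeat an event term, and 15.17 calls these reactions severe skin rash. A site could reasonably apply the mandatory stop there. That reading helps at Grade 4 only, and the table does not state it.

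Two sources are outside the documents. Grading follows CTCAE version 4.0, so it is not shown here that TEN or DRESS can be graded 3. The Investigator's Brochure, to which 15.17 refers for managing toxicity, may contain a stop rule. The point is therefore about what the protocol tables say, not about whether any guidance exists.

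A reader might infer that the protocol orders ixazomib to be restarted after SJS. The documents do not support that. Table 8.3 ends all study treatment for Grade 3-4 SJS under a heading that covers every phase, and 8.0 expects the tables to specify when a patient may not continue on the other drugs. What remains for SJS is an ambiguity between two tables, limited to cases attributed to ixazomib alone.

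**Conclusion.** The point holds for TEN and DRESS: both are listed for both drugs, neither table has a row for them, and the default rows permit a restart or leave stopping optional. For SJS it holds only as an unclear overlap between the tables when ixazomib alone is blamed.

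The size is minor and the change is a cheap improvement. The reactions are rare, the trial is small, the text is strict only in cycles 1-2, and investigator discretion applies throughout. The primary endpoint analysis is not affected. The accrual suspension rule in 16.42 counts related Grade 4 or higher non-hematologic events, but it protects later patients and not the one affected.

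The conclusion assumes that sites apply the default rows to events without their own row. The Grade 3 part also assumes that such an event can be graded 3; if TEN or DRESS cannot be, only the Grade 4 default matters for that event.

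**What to change.** Make four edits at the next amendment:

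- Add a Table 8.2 row for SJS, TEN or DRESS of Grade 3 or above: permanently discontinue ixazomib and remove the patient from all study treatment, in every phase.
- Add TEN and DRESS to the SJS row of Table 8.3.
- Exclude the three events from the default Grade 3 and Grade 4 rows of Table 8.2 and from the default non-hematologic row of Table 8.3.
- In the SJS sentence of the rash subsection 9.9a, refer to the new row.

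Sample size, decision rule and analysis stay as they are. The cost is that a rare patient loses the option of rechallenge, an option that Table 8.3 already removes for Grade 3-4 SJS where its row applies.
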